### 8.2.5 Study Follow-up

Follow-up will be evaluated in two ways. With an 'intention-to-treat' analysis, patients will be followed for all available time after they initiate a medication, irrespective of whether they discontinue the medication or not, or whether they switch to an alternate medication or not. Follow-up begins the day after the index date and ends at first occurrence of: (a) the outcome of interest, (b) disenrollment from a health plan, or (c) end of study period.

With a 'per-protocol analysis' patients are followed for as long as they are actively taking the medication of interest during the follow-up period. Follow-up begins the day after the index date and ends at first occurrence of: (a) the outcome of interest, (b) disenrollment from the health plan, (c) discontinuation of study medication, (d) switching to the alternate medication, or (e) administrative end of study. When a gap greater than the allowable gap of 30 days is encountered, discontinuation of study medication occurs at the end of the last prescription which includes the days supply (+60 day extension). Censoring due to switching will occur for the new user cohorts in this study when the following conditions are met:

- (1) For new users of erenumab-aooe, initiation of any other medication targeting the CGRP pathway (galcanezumab-gnlm, fremanezumab-vfrm, eptinezumab-jjmr, ubrogepant, rimegepant) during the follow-up period.
- (2) For new users of other mAbs targeting the CGRP pathway, initiation of erenumab-aooe, ubrogepant, or rimegepant during the follow-up period.
- (3) For new users of the SOC migraine preventive medications (anti-epileptics), initiation of any medication targeting the CGRP pathway (erenumab-aooe, galcanezumab-gnlm, fremanezumab-vfrm, eptinezumab-jjmr, ubrogepant, rimegepant) during the follow-up period.
- (4) For new users of onabotulinumtoxinA, initiation of any medication targeting the CGRP pathway (erenumab-aooe, galcanezumab-gnlm, fremanezumab-vfrm, eptinezumab-jjmr, ubrogepant, rimegepant) during the follow-up period.

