Follow-up will be evaluated in two ways. With an 'intention-to-treat' analysis, patients will be followed for all available time after they initiate a medication, irrespective of whether they discontinue the medication or not, or whether they switch to an alternate medication or not. Follow-up begins the day after the index date and ends at first occurrence of: (a) the outcome of interest, (b) disenrollment from a health plan, or (c) end of study period. With a 'per-protocol analysis' patients are followed for as long as they are actively taking the medication of interest during the follow-up period. Follow-up begins the day after the index date and ends at first occurrence of: (a) the outcome of interest (each outcome will be assessed independently), (b) disenrollment from the health plan, (c) discontinuation of study medication, (d) switching to an alternate medication, or (e) administrative end of study. For the erenumab-acce and other mAbs targeting the CGRP cohorts, switching occurs when any preventive or acute medication other than the index medication targeting the CGRP pathway is initiated during the follow-up period. For the SOC migraine preventive medications (anti-epileptics) and onabotulinumtoxinA cohorts, switching occurs at initiation of any preventive or acute medication that targets the CGRP pathway during the follow-up period.

- Variables
  - Outcome Variables

The outcomes of interest are hypertension, acute MI, and stroke, which will be identified using ICD-10-CM diagnosis codes.

- Hypertension occurrence of one inpatient (IP) diagnosis, one emergency room (ER) diagnosis, or one outpatient (OP) diagnosis during the follow-up period.
- (2) Acute MI occurrence of one diagnosis in the IP setting during the follow-up period.

- (3) Stroke, including both ischemic stroke and hemorrhagic stroke occurrence of one diagnosis in the IP setting during the follow-up period.
- Exposure Variables New users of:
  - (1) erenumab-aooe,
  - (2) other mAbs targeting the CGRP pathway (fremanezumab-vfrm, galcanezumab-gnlm, eptinezumab-jjmr),
  - (3) selected SOC migraine preventive medications (anti-epileptics) (topiramate, valproic acid, divalproex sodium) which are approved by the Food and Drug Administration (FDA) for the prevention of migraine, and
  - (4) OnabotulinumtoxinA, which is also approved by the FDA for the prevention of migraine.
- Other Covariates

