# 8.9.1.3 Selection Bias

Differential loss to follow-up is a type of selection bias that poses a potential threat to the internal validity of any study, including randomized studies. Loss to follow-up can be broadly conceptualized as any termination of treatment prior to the administrative end of the study, including, but not limited to, discontinuation of assigned treatment, switching to the alternate study arm, drop-out as a result of change in health plan, drop-out due to illness/frailty, etc. If all disenrollment occurred at random (eg, because of the loss of a health plan at the end of the calendar year), there would be loss in precision, but no increase in bias of the effect estimate. In most studies using claims data, however, we assume that health plan disenrollment, particularly mid-year disenrollment, does not occur at random. Under these circumstances, we must use methods such as IP weights to account for differential health plan disenrollment. These methods have been

described earlier and assume that we are able to identify strong confounders of disenrollment / switching / discontinuation and the outcome. Such covariates can be difficult to identify in claims data, but recent research has elucidated several baseline predictors of health plan disenrollment (Butler et al, 2019). More relevant predictors may be time-varying covariates (such as medical history indicators) that occur proximate to health plan disenrollment. We will explore inclusion of time-varying covariates in our censoring models, to address differential health plan disenrollment / switching to an alternate CGRP mAb / discontinuation of study medication.

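### Per-protocol censoring for switching is one-sided in erenumab versus anti-epileptics and erenumab versus onabotulinumtoxinA, with a bias of uncertain direction

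*Protocol*

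**What the plan says.** Section 8.2.5 of the Protocol ends per-protocol follow-up at, among other events, "c) discontinuation of study medication, (d) switching to the alternate medication, or (e) administrative end of study". It then lists what counts as switching in each cohort:

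- Rule (1), erenumab: "For new users of erenumab-aooe, initiation of any other medication targeting the CGRP pathway".
- Rule (2), other CGRP antibodies: "For new users of other mAbs targeting the CGRP pathway, initiation of erenumab-aooe, ubrogepant, or rimegepant during the follow-up period".
- Rule (3), anti-epileptics: "For new users of the SOC migraine preventive medications (anti-epileptics), initiation of any medication targeting the CGRP pathway".
- Rule (4), onabotulinumtoxinA: "For new users of onabotulinumtoxinA, initiation of any medication targeting the CGRP pathway".

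Discontinuation is a separate censoring event. Once a gap exceeds 30 days, "discontinuation of study medication occurs at the end of the last prescription which includes the days supply (+60 day extension" (the parenthesis closes there). A comment in the ENCePP checklist (Appendix B) adds 30 and 60 days to get a 90-day window and relates that window to the half-life of erenumab.

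Two other places describe switching. Section 8.9.1.3 includes "switching to the alternate study arm, drop-out as a result of change in health plan" in a general list of ways to be lost, and closes by naming a move to a different CGRP antibody. For the two CGRP antibody cohorts, the Abstract says that "switching occurs when any preventive or acute medication other than the index medication targeting the CGRP pathway is initiated during the follow-up period".

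**The concern.** In the second contrast (erenumab versus anti-epileptics) and the third (erenumab versus onabotulinumtoxinA), the arms follow different strategies. The comparator arm is the comparator without erenumab. The erenumab arm is erenumab with or without a newly started comparator. Some erenumab person-time may then carry the risk of the drug it is being compared with.

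This is a safety comparison for acute MI and stroke. Section 8.7.2.4 says the comparison accounts for switching and builds censoring weights for it, so the rule feeds directly into the estimate. Negative control outcomes are unlikely to reveal the problem: they are chosen because treatment should not cause them, and mixing two treatments that do not affect an outcome leaves its risk ratio at the null.

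There is also a programming problem. The Abstract and Section 8.2.5 can lead two programmers to different censoring dates for the same patient.

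**Working it through.** **Step 1. The rules side by side.**

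| Event during follow-up | Section 8.2.5 |
|---|---|
| Anti-epileptic user starts erenumab | Censored (rule 3) |
| Erenumab user starts topiramate, valproic acid or divalproex | Not censored for switching (rule 1) |
| OnabotulinumtoxinA user starts erenumab | Censored (rule 4) |
| Erenumab user starts onabotulinumtoxinA | Not censored for switching (rule 1) |
| Fremanezumab user moves to galcanezumab | Not censored for switching (rule 2) |

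The Abstract refers to a drug other than the index medication. If that means the individual drug, the last row becomes censored, which conflicts with rule (2). The two agree only if the index medication means the whole other-antibody group, and the text does not say so. The Abstract sentence can also be read as censoring on any other preventive, which would conflict with rule (1).

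**Step 2. How long mixed time can last.** If the comparator replaces erenumab, the discontinuation rule ends follow-up at the remaining days supply plus 60 days. Anyone counted longer is still filling erenumab, so that time is concurrent use.

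**Step 3. Replacement.** The Protocol gives no switch rate and no bias figure, so there is nothing to reproduce and the inputs here are assumptions. Let f be the share of erenumab person-time after the comparator has replaced erenumab, and treat that time as carrying comparator risk only. For a rare outcome, approximately:

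observed RR = RR × (1 − f) + f.

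With misclassified time confined to the extension, f = (proportion switching) × 60 / (mean on-treatment days). Assume 10% to 30% switch and mean on-treatment time is 180 to 365 days:

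- Lowest: f = 0.10 × 60 / 365 = 0.016. RR 2.0 becomes 2.0 × 0.984 + 0.016 = 1.98.
- Highest: f = 0.30 × 60 / 180 = 0.10. RR 2.0 becomes 2.0 × 0.90 + 0.10 = 1.90.

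Remaining supply at the time of the switch would add to f. A residual erenumab effect during the extension would reduce the attenuation.

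**Step 4. Add-on use.** Let E and C be the effects of erenumab and the comparator on the outcome against no drug, acting multiplicatively. The true RR is E/C, and:

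observed RR = (E/C) × (1 − f + f × C).

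Taking f from 5% to 30%, also assumed:

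- E = 2, C = 1: the true 2.0 stays 2.0.
- E = 2, C = 1.2: the true 1.667 becomes 1.68 to 1.77, away from the null.
- E = 2, C = 0.8: the true 2.5 becomes 2.48 to 2.35, toward the null.

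The one-sidedness follows from the text. The direction of bias does not.

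**The case against.** The strongest defence is that the list applies one principle throughout. Starting a CGRP-pathway drug from outside the index group censors in all four cohorts, and starting any other preventive censors in none. The list follows the general statement in 8.2.5 and can be read as defining switching rather than failing to implement it. Section 8.9.1.3 ends with CGRP-only wording, and the study's rationale is CGRP blockade. Erenumab patients may already be taking a comparator drug at index (Section 8.2.2.2), and Appendix D includes anti-epileptics and botulinum toxins at baseline in both models. This stands as far as it goes: a CGRP-only rule is a possible choice of estimand. But the Protocol never states or justifies it as such, and it does not fit the phrases about the alternate medication or the alternate arm.

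Section 8.2.2 also draws the comparator cohorts from patients left after the antibody cohorts are formed. Read literally, many patients who later start erenumab never enter a comparator cohort, so rules (3) and (4) would seldom act on them. Their crossover is then removed by selection instead of censoring. It is still removed from one side only.

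A reader might infer more: that erenumab users who start a comparator simply stay counted as erenumab, that this pulls the risk ratio toward the null, and that the dilution is large. For example, after one 30-day fill and an immediate switch, 60 of 90 counted days (67%) fall after supply ends. The documents do not support this reading. It leaves out the discontinuation rule. It treats a window that Appendix B relates to the half-life as wholly unexposed. It generalises from one hypothetical patient. Attenuation of RR 2.0 to 1.8 or 1.7 would need 20% or 30% of person-time to be pure comparator time, and nothing in the Protocol suggests that.

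**Conclusion.** The point holds in a limited form. In the per-protocol version of the second and third contrasts, movement from comparator to erenumab is censored and movement from erenumab to comparator is not, so the contrasts are not like for like. Under replacement, with misclassified time confined to the 60-day extension, the bias is toward the null and small: about 1.98 to 1.90 for a true risk ratio of 2.0. That range rests on assumed switching proportions and treatment durations and on no residual erenumab effect. Under add-on use the risk ratio is unchanged if the comparator does not affect the outcome, and otherwise may move in either direction. A general claim of dilution is therefore not justified. The intention-to-treat analysis ignores switching in every cohort and is unaffected, but it does not answer the on-treatment question. Separately, the Abstract and rule (2) as worded give different follow-up for a patient who moves between two drugs in the other-antibody cohort.

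**What to change.** Make the switching rule specific to each contrast and symmetric:

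- Erenumab versus anti-epileptics: also censor erenumab users at the earliest claim for topiramate, valproic acid or divalproex not in use at index.
- Erenumab versus onabotulinumtoxinA: also censor them at the earliest onabotulinumtoxinA claim, if not in use at index.
- Define in advance what counts as in use at index, and include the new event in the censoring model already planned in Section 8.7.2.4.

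If the CGRP-only rule is what the sponsor intends, say so as the estimand and run the symmetric rule beside it as a sensitivity analysis. In either case, state that comparator use already present at index remains in the erenumab arm and is adjusted for only at baseline.

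Reconcile the Abstract, Section 8.2.5 and Section 8.9.1.3, including whether a move such as fremanezumab to galcanezumab is a censoring event.

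The cost is protocol wording and one more censoring date per contrast, from drugs already coded in Appendix C. The drawback is somewhat shorter per-protocol follow-up for erenumab, including for patients who add the comparator and continue erenumab.

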#### 8.3 Variables

#### 8.3.1 Exposure Assessment

The cohorts of erenumab-aooe, other mAbs targeting the CGRP pathway (galcanezumab-gnlm, fremanezumab-vfrm, eptinezumab-jjmr), select SOC migraine preventive medications (anti-epileptics: topiramate, valproic acid, divalproex sodium), and onabotulinumtoxinA initiators will be identified as described in Section 8.2. New use of medications will be based on NDCs or HCPCS codes as captured in the pharmacy tables within the MarketScan® claims database. The list of NDCs and HCPCS codes that will be used for cohort identification is provided in Appendix C.

### 8.3.2 Outcome Assessment

The outcomes of interest are hypertension, acute MI, and stroke, which will be identified within the MarketScan® claims database using ICD-10-CM diagnosis codes. The following algorithms will be used for each of the outcomes:

- Hypertension occurrence of one inpatient (IP) diagnosis, one emergency room (ER) diagnosis, or one outpatient (OP) diagnosis during the follow-up period.
- (2) Acute MI occurrence of one diagnosis in the IP setting during the follow-up period.
- (3) Stroke, including both ischemic stroke and hemorrhagic stroke occurrence of one diagnosis in the IP setting during the follow-up period.

All outcomes will be assessed separately starting from the index date through the end of follow-up as described in Section 8.2.5. Only the first (incident) event for each outcome will be included in the analysis. The ICD-10-CM diagnosis codes for hypertension acute MI, and stroke are provided in Appendix C. The validation studies supporting the algorithms and ICD-10-CM diagnosis codes for the outcomes evaluated in this study are

provided in Section 8.3.4. The negative control outcomes that will be used to evaluate exchangeability between study cohorts for the comparative analyses are described in Section 8.7.2.4.

#### 8.3.3 Covariate Assessment

 Table 1 below provides categorization of a set of baseline covariates that will be used to describe the study population.

Variable	Measurement	
Demographics		
Patient age (years)	Continuous, and categorized into five categories (18-24, 25-34, 35-44, 45-54, 55-64)	
Patient gender	0/1 indicator (female)	
Comorbidities		
Diabetes mellitus	0/1 indicator at study entry	
Hypercholesterolemia	0/1 indicator at study entry	
Hypertension	0/1 indicator at study entry	
Liver disease / Cirrhosis	0/1 indicator at study entry	
Depression	0/1 indicator at study entry	
Chronic Obstructive Pulmonary Disease (COPD)	0/1 indicator at study entry	
Renal Disease	0/1 indicator at study entry	
Malignancy (Other Than Skin)	0/1 indicator at study entry	
Cardiac arrhythmia	0/1 indicator at study entry	
Asthma	0/1 indicator at study entry	
Human immunodeficiency virus (HIV)	0/1 indicator at study entry	
Lupus	0/1 indicator at study entry	
Psoriasis	0/1 indicator at study entry	
Atopic dermatitis	0/1 indicator at study entry	
Rheumatoid arthritis (RA)	0/1 indicator at study entry	
Epilepsy/Seizure/Convulsions	0/1 indicator at study entry	

 Table 1. Baseline Covariates

Footnotes defined on last page of table

Page 1 of 5

Variable	Measurement
Comorbidities (continued)	
Anxiety	0/1 indicator at study entry
Depression	0/1 indicator at study entry
Peripheral Artery Disease	0/1 indicator at study entry
Venous thromboembolism	0/1 indicator at study entry
Critical limb ischemia	0/1 indicator at study entry
Myocardial Ischemia	0/1 indicator at study entry
Congestive heart failure	0/1 indicator at study entry
Acute myocardial infarction	0/1 indicator at study entry
Unstable angina	0/1 indicator at study entry
Prinzmetal angina	0/1 indicator at study entry
Other and unspecified angina pectoris	0/1 indicator at study entry
Acute atrial fibrillation	0/1 indicator at study entry
Paroxysmal atrial fibrillation	0/1 indicator at study entry
Acute ventricular fibrillation	0/1 indicator at study entry
Premature atrial contractions	0/1 indicator at study entry
Acute ventricular tachycardia	0/1 indicator at study entry
Coronary revascularization	0/1 indicator at study entry
Ischemic/hemorrhagic stroke	0/1 indicator at study entry
Sub-arachnoid stroke	0/1 indicator at study entry
Unspecified stroke	0/1 indicator at study entry
Transient ischemic attack	0/1 indicator at study entry
Other acute cerebrovascular events	0/1 indicator at study entry
Other ischemic cerebrovascular events	0/1 indicator at study entry
Migraine Features	
Chronic Migraine (without Aura)	0/1 indicator at study entry
Migraine Aura	0/1 indicator at study entry
Healthcare Utilization	
Number of ambulatory visits	Continuous, and categorized based on distribution
Number of emergency room visits	Continuous, and categorized based on distribution
Number of inpatient hospital stays	Continuous, and categorized based on distribution

#### Table 1. Baseline Covariates

Footnotes defined on last page of table

Page 2 of 5

Variable	Measurement	
Concomitant Medications		
Overall Medication Utilization a		
Number of unique generic medications dispensed	Continuous, and categorized based on distribution	
Number of unique drug classes dispensed	Continuous, and categorized based on distribution	
Preventive Migraine Medications		
Anti-epileptic agents	0/1 indicator at study entry for Carbamazepine, Gabapentin, Levetiracetam, Pregabalin, Topiramate, valproic acid, divalproex sodium, Zonisamide	
Anti-hypertensive, beta blockers	0/1 indicator at study entry for Atenolol, Bisoprolol, Metoprolol, Nadolol, Nebivolol, Pindolol, Propranolol, Timolol	
Anti-hypertensive, calcium channel blockers	0/1 indicator at study entry for Flunarizine, Verapamil,	
Anti-hypertensive, other	0/1 indicator at study entry for Candesartan, Clonidine, Lisinopril	
Anti-depressants, serotonin norepinephrine reuptake inhibitors	0/1 indicator at study entry for Duloxetine, Desvenlafaxine, Venlafaxine	
Anti-depressants, tri-cyclics	0/1 indicator at study entry for Amitriptyline, Desipramine, Doxepin, Imipramine, Nortriptyline, Protriptyline	
Anti-depressants, selective serotonin reuptake inhibitors	0/1 indicator at study entry for Escitalopram, Citalopram, Sertraline	
Botulinum toxin	0/1 indicator at study entry for AbobotulinumtoxinA, IncobotulinumtoxinA, OnabotulinumtoxinA, RimabotulinumtoxinB	
Other migraine preventive agents	0/1 indicator at study entry for Carisoprodol, Cyproheptadine, Guanfacine, Memantine, Methysergide, Milnacipran, Tizanidine	
Acute Migraine Medications		
Ergotamines	0/1 indicator at study entry for Dihydroergotamine mesylate, Ergotamine tartrate, Ergotamine tartrate + caffeine, Ergotamine tartrate + caffeine + belladonna + pentobarbital	
Triptans	0/1 indicator at study entry for Almotriptan, Eletriptan, Frovatriptan, Naratriptan, Rizatriptan, Sumatriptan (with and without naproxen), Zolmitriptan	

#### Table 1. Baseline Covariates

Footnotes defined on last page of table

Page 3 of 5

Variable	Measurement	
Acute Migraine Medications (continued)		
NSAIDS	0/1 indicator at study entry for Aspirin, Celecoxib, Diclofenac, Diflunisal, Etodolac, Fenoprofen, Flurbiprofen, Ibuprofen, Indomethacin, Ketoprofen, Ketorolac, Magnesium salicylate, Meclofenamic Acid, Mefanamic Acid, Meloxicam, Nabumetone, Naproxen, Oxaprozin, Piroxicam, Rofecoxib, Salsalate, Sulindac, Tolmetin, Valdecoxib	
Opioids	0/1 indicator at study entry for Codeine, Fentanyl, Hydrocodone, Hydromorphone, Morphine Sulfate, Oxycodone, Oxymorphone, Tramadol, Alfentanil, Buprenorphine, Butorphanol tartrate, Dezocine, Dihydrocodeine, Levomethadyl, Levorphanol, Meperidine, Methadone, Nalbuphine, Opium / belladonna alkaloids / opium alkaloids, Pentazocine, Propoxyphene, Remifentanil, Sufentanil, Tapentadol	
NonNSAID NonOpioid Analgesics	0/1 indicator at study entry for Acetaminophen, Baclofen, Butalbital, Ziconotide	
Other acute migraine treatment	0/1 indicator at study entry for Lasmiditan	
Other Medications		
Contraceptives	0/1 indicator at study entry	
Anti-hypertensives		
Aldosterone antagonist	0/1 indicator at study entry	
Angiotensin receptor blockers	0/1 indicator at study entry	
Angiotensin-converting enzyme (ACE) inhibitors	0/1 indicator at study entry	
Beta-blockers	0/1 indicator at study entry	
Calcium-channel blockers	0/1 indicator at study entry	
Diuretics	0/1 indicator at study entry	
Other anti-hypertensives	0/1 indicator at study entry	
Anti-coagulants	0/1 indicator at study entry	
Anti-platelets	0/1 indicator at study entry	
Lipid-lowering agents		
Statins	0/1 indicator at study entry	
Non-statins	0/1 indicator at study entry	

